3.0 Patient Eligibility

3.1 Inclusion Criteria

- 3.1.1 Patients with newly diagnosed double hit in first complete remission, anytime during the first 3 months after chemoimmunotherapy followed by autologous stem cell transplantation if there was no evidence of progression.
- 3.1.2 Double hit lymphoma is defined as B-cell lymphoma with genetic abnormalities involving A) and in addition, B) and/or C):
 - A) C-MYC arrangement or amplification by FISH study.
 - B) BCL2 rearrangement or amplification by FISH study.
 - C) BCL6 rearrangement or amplification by FISH study.
- 3.1.3 ANC \geq 1,000, platelets \geq 75,000.
- 3.1.4 AST and/or ALT < 3 times the ULN.
- 3.1.5 Creatinine clearance > 30 ml/min (Cockcroft-Gault formula using ideal body weight).
- 3.1.6 Male or female age \geq 18 years.
- 3.1.7 ECOG performance status \leq 2.
- 3.1.8 Willing and able to participate in all required evaluations and procedures in this study protocol including swallowing capsules without difficulty.
- 3.1.9 Ability to understand the purpose and risks of the study and provide signed and dated informed consent and authorization to use protected health information.
- 3.1.10 Patient should preferably have received a pre-transplant conditioning with rituximab and Carmustine/Etoposide/Cytarabine/Melphalan/Rituxan (BEAM/R) . Other regimens which are similar may be accepted at the discretion of the PI.

3.2 Exclusion Criteria

- 3.2.1 Prior chemotherapy within 3 weeks, nitrosoureas (carmustine) within 6 weeks, therapeutic anticancer antibodies within 4 weeks, radio- or toxin-immunoconjugates within 10 weeks, radiation therapy within 3 weeks, or major surgery within 2 weeks of first dose of study drug.
- 3.2.2 Relapsed within three months post-transplant.
- 3.2.3 History of other malignancies within the past year except for treated basal cell or squamous cell skin cancer or in situ cervical cancer.
- 3.2.4 Known CNS lymphoma.

- 3.2.5 Clinically significant cardiovascular disease such as uncontrolled or symptomatic arrhythmias, congestive heart failure, or myocardial infarction within 6 months of screening, or any Class 3 (moderate) or 4 (severe) cardiac disease as defined by the New York Heart Association Functional Classification.
- 3.2.6 Requires treatment with a strong cytochrome P450 (CYP)3A inhibitor (i.e. Voriconazole, posaconazole, itraconazole, clarithromycin, etc.) or inducer (carbamazepine, rifampin, phenytoin, etc.).
- 3.2.7 AST and/or ALT \geq 3 times the ULN.
- 3.2.8 Malabsorption syndrome, disease significantly affecting gastrointestinal function, or resection of the stomach or small bowel or symptomatic ulcerative colitis, symptomatic inflammatory bowel disease, or partial or complete bowel obstruction.
- 3.2.9 Known history of human immunodeficiency virus or active infection with hepatitis C virus or hepatitis B virus or any uncontrolled active systemic infection.
- 3.2.10 Positive pregnancy test in women of childbearing potential.
- 3.2.11 Lactating or pregnant or will not agree to use contraception during the study and for 30 days after the last dose of study drug if sexually active and able to bear children.
- 3.2.12 Concomitant use of warfarin or other Vitamin K antagonists.

4.0 Treatment Plan

- 4.1 Ibrutinib will be started at a daily dose of 560 mg po daily.
- 4.2 Patients will continue on Ibrutinib until relapse, or AE not managed by dose adjustment, or upon completion of 3 years on ibrutinib. Dose will be adjusted should cytopenia or other non-hematologic toxicity occur (Sections 4.4 and 4.5).
- 4.3 For patients requiring surgery, ibrutinib should be held 3 to 7 days prior to surgery (depending on surgery type and bleeding risk) and hold for 7 days post-surgery.
- 4.4 Parameters to hold/interrupt ibrutinib:
 - Grade \geq 3 neutropenia with fever.
 - Grade 4 neutropenia lasting $>$ 7 days (despite use of GCSF).
 - Grade 3 or 4 platelet counts $<$ 50,000/microL in presence of significant bleeding. In subjects with baseline thrombocytopenia, a platelet decrease of 50 to 75% in presence of significant bleeding.
 - Grade 4 platelets $<$ 25,000/microL or, in subjects with baseline thrombocytopenia, decrease of $>$ 75% from baseline or $<$ 20,000/microL, whichever is higher.
 - Any Grade \geq 3 non-hematologic toxicity.

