6.2.4 Antiplatelet Agents and Anticoagulants

Warfarin or vitamin K antagonists should not be administered concomitantly with ibrutinib. Supplements such as fish oil and vitamin E preparations should be avoided. Use ibrutinib with caution in subjects requiring other anticoagulants or medications that inhibit platelet function. Subjects with congenital bleeding diathesis have not been studied. Ibrutinib should be held at least 3 to 7 days pre- and post-surgery depending upon the type of surgery and the risk of bleeding (see Section 6.4).

Subjects requiring the initiation of therapeutic anticoagulation therapy (eg, atrial fibrillation), consider the risks and benefits of continuing ibrutinib treatment. If therapeutic anticoagulation is clinically indicated, treatment with ibrutinib should be held and not be restarted until the subject is clinically stable and has no signs of bleeding. Subjects should be observed closely for signs and symptoms of bleeding. No dose reduction is required when study drug is restarted.

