6.4.1 Minor Surgical Procedures

For minor procedures (such as a central line placement, needle biopsy, thoracentesis, or paracentesis) ibrutinib should be held for at least 3 days prior to the procedure and should not be restarted for at least 3 days after the procedure. For bone marrow biopsies that are performed while the subject is on ibrutinib, it is not necessary to hold ibrutinib for these procedures.

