6.4.2 Major Surgical Procedures

For any surgery or invasive procedure requiring sutures or staples for closure, ibrutinib should be held at least 7 days prior to the intervention and should be held at least 7 days after the procedure and restarted at the discretion of the investigator when the surgical site is reasonably healed without serosanguineous drainage or the need for drainage tubes.

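### Section 4.3 sets a flat 7-day hold after all surgery, with no healing condition and no reference to Section 6.4, and so departs from Sections 6.2.4 and 6.4

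*Combined protocol and SAP*

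**What the plan says.** The protocol gives perioperative hold instructions in three places.

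- **Section 4.3 (Treatment Plan).** When a patient is to have an operation, the rule reads: "ibrutinib should be held 3 to 7 days prior to surgery (depending on surgery type and bleeding risk) and hold for 7 days post-surgery". Judgement about surgery type and bleeding risk is attached to the period before surgery only. There is no reference to Section 6.4.
- **Section 6.2.4 (antiplatelet agents and anticoagulants).** "Ibrutinib should be held at least 3 to 7 days pre- and post-surgery depending upon the type of surgery and the risk of bleeding". Here the judgement applies on both sides of the operation, and the sentence sends the reader to Section 6.4.
- **Section 6.4 (surgeries and procedures).** This section sets the hold by class of procedure:
  - Minor (6.4.1): "ibrutinib should be held for at least 3 days prior to the procedure", and the drug "should not be restarted for at least 3 days after the procedure". For bone marrow biopsy, "it is not necessary to hold ibrutinib for these procedures".
  - Major, meaning anything closed with sutures or staples (6.4.2): "ibrutinib should be held at least 7 days prior to the intervention and should be held at least 7 days after the procedure". Restart is then at the investigator's discretion, once the site is reasonably healed, with no blood-stained drainage and no need for a drain.
  - Emergency (6.4.3): after the procedure, until the site is reasonably healed or for at least 7 days, whichever takes longer.

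The introduction to Section 6.4 says that the drug may raise the risk of bleeding at invasive procedures. Section 2.8.8.2 reports major hemorrhages, some of them fatal, and also refers to Section 6.4 for surgery.

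**The concern.** A physician who opens the Treatment Plan finds what looks like a complete rule for surgery, with nothing to show that a more detailed one follows in Section 6.4. If the two rules differ for the same patient, complying with one can be a deviation from the other, and a patient's restart date depends on which page was read.

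The protocol itself names bleeding around surgery as a risk of the drug. Treatment may last 3 years under Section 4.2, so operations and procedures on treatment are foreseeable. What is at stake is clear, consistent handling of individual patients, not the statistical design.

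**Working it through.** There is no design figure to reproduce: the point does not depend on alpha, power, effect size or sample size. The check sets the rules side by side, by class of procedure and by period. Days are counted without the day of the procedure.

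| Situation | Section 4.3 | Section 6.2.4 | Section 6.4 |
|---|---|---|---|
| Minor, before | 3 to 7, by type and risk | at least 3 to 7, by type and risk | at least 3 (6.4.1) |
| Minor, after | 7 | at least 3 to 7, by type and risk | at least 3 (6.4.1) |
| Sutures or staples, before | 3 to 7, by type and risk | at least 3 to 7, by type and risk | at least 7 (6.4.2) |
| Sutures or staples, after | 7, no healing condition | at least 3 to 7, by type and risk | at least 7, and site reasonably healed (6.4.2) |
| Emergency, after | no separate rule, so 7 | no separate rule | longer of healing and at least 7 (6.4.3) |

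**Step 1: Section 6.2.4 against Section 6.4.** The ends of the 6.2.4 range, 3 and 7, are the minimums that 6.4.1 and 6.4.2 assign to minor and major procedures, and 6.2.4 cites 6.4. The two are consistent: a summary and its detail.

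**Step 2: after a minor procedure.** Section 6.4.1 permits restart from day 3, while a literal 4.3 does not permit it until 7 days have passed. The difference is 7 − 3 = 4 days. A restart on day 3, 4, 5 or 6 meets 6.4.1 and departs from 4.3. With 3 days held beforehand, the shortest total hold is 3 + 7 = 10 days under 4.3 and 3 + 3 = 6 days under 6.4.1.

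**Step 3: after a major or emergency procedure.** Take a patient whose site is not healed at day 7. The hold in 4.3 is complete, but the restart condition in 6.4.2 or 6.4.3 is not met. The documents give no upper limit for healing time, so this gap cannot be put in days.

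**Step 4: before a sutured procedure.** There are two readings of surgery type in 4.3.
- If it means the 6.4 classes, a sutured procedure takes the 7-day end of the range. The total is 7 + 7 = 14 days, the same as the 6.4.2 minimum, and there is no gap.
- If it is left to free judgement, 4.3 permits 3 days where 6.4.2 requires at least 7, a gap of 7 − 3 = 4 days. The shortest total is 3 + 7 = 10 days, against at least 7 + 7 = 14.

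Section 4.3 does not say which reading is meant.

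**The case against.** Several points on the other side are sound, and they rule out stronger readings that a reader might infer.

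- **That all three places contradict one another.** They do not. Section 6.2.4 cites 6.4 and agrees with it; Section 4.3 alone is the outlier.
- **That 4.3 allows 3 days before any surgery.** This drops its qualifier. The period depends on surgery type and bleeding risk, and the two ends match the 6.4 minimums. The 4-day gap before surgery is therefore conditional on how 4.3 is read.
- **That a 7-day hold after a minor procedure breaches 6.4.1.** It does not, because 6.4.1 sets a minimum. The conflict arises only when the shorter hold that 6.4.1 permits is used. If the 7 days in 4.3 are also taken as a minimum, a long enough hold satisfies every section, but the shorter option in 6.4.1 is then never available.
- **That local physicians will act on 4.3 alone.** Section 7.3 reserves protocol treatment decisions to the study center's physician, who must approve changes of dose or schedule beforehand. The point rests on that physician facing two texts.
- **That the bleeding data are distorted.** The documents do not show this. The definition of major hemorrhage in Section 10.3.5 does not depend on the length of a hold, and Section 9.0 plans no comparison of bleeding.

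One could also argue that surgery in 4.3 excludes central lines, needle biopsies and the like, since the introduction to 6.4 speaks separately of surgery and invasive procedures. But 6.4.1 is headed as minor surgical procedures. Moreover, 6.2.4 speaks of the post-surgery period, as 4.3 does, and lets it vary by type where 4.3 does not. The healing condition is also untouched by this argument. So the argument narrows the minor-procedure conflict but does not remove the inconsistency.

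**Conclusion.** The inconsistency is real and sits in Section 4.3. Two conflicts follow from its literal wording: up to 4 days in the earliest restart after a minor procedure, and a missing healing condition after major and emergency procedures. The first assumes that surgery in 4.3 includes the minor surgical procedures of 6.4.1; the second needs no such assumption. A third, 4 days before sutured procedures, exists only if surgery type in 4.3 does not mean the 6.4 classes.

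The point should be corrected because it concerns the handling of a risk that the protocol itself names. It does not touch the primary endpoint or the power. No view is taken on which hold is right.

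**What to change.** Reconcile Section 4.3 with Sections 6.2.4 and 6.4. Keep one set of instructions, arranged by class of procedure, and let 4.3 refer to it instead of restating periods of its own. The agreed text should say whether surgery includes the minor procedures of 6.4.1, and whether restart depends on healing as well as on elapsed days. Section 6.2.4 already refers to 6.4 and need only be checked against the agreed text. The content of the rules is for the clinical investigators to decide.

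The cost is protocol wording, through the amendment route in Section 11.0. Sample size, endpoint and analysis stay as they are.

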4.5 Toxicity Management

Toxicity occurrence	Action	Toxicity not related to study drug	Toxicity related to study drug
First	Hold drug until resolution to grade I or to baseline.	Restart at original dose	Restart at 420 mg/day
Second	Hold drug until resolution to grade I or to baseline.	Restart at 420 mg/day	Restart at 280 mg/day
Third	Hold drug until resolution to grade I or to baseline.	Restart at 280 mg/day	Restart at 140 mg/day
Fourth	Hold drug until resolution to grade I or to baseline.	Stop medication, do not re-challenge	Stop medication, do not re-challenge

If the dose of ibrutinib/placebo is reduced, at the investigator's discretion, the dose of ibrutinib may be re-escalated after 2 cycles of a dose reduction in the absence of a recurrence of the toxicity that led to the reduction. Dose changes must be recorded in the Dose Administration eCRF.

Leukocytosis/Leukostasis

A high number of circulating malignant cells (>400000/mcL) may confer increased risk of leukostasis; these subjects should be closely monitored. Administer supportive care such as hydration and/or leukapheresis as indicated. Ibrutinib may be temporarily held, and investigator should be contacted.

Dose Modification for Hepatic Impaired Subjects

Ibrutinib is metabolized in the liver and therefore subjects with clinically significant hepatic impairment at the time of screening (Child- Pugh class B or C) are excluded from study participation. For subjects who develop mild liver impairment while on study (Child-Pugh class A), the recommended dose reduction for ibrutinib is to a level of 280 mg daily (two capsules). For subjects who develop moderate liver impairment while on study (Child-Pugh class B), the recommended dose reduction is to a level of 140 mg daily (one capsule). Subjects who develop severe hepatic impairment (Child-Pugh class C) must hold study drug until resolved to moderate impairment (Child-Pugh class B) or better. Monitor subjects for signs of toxicity and follow dose modification guidance as needed (Section 4.5).

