5.1.3 Dose and Administration

Ibrutinib 560 mg (4 x 140-mg capsules) is administered orally once daily. The capsules are to be taken around the same time each day with 8 ounces (approximately 240 mL) of water. The capsules should be swallowed intact and patients should not attempt to open capsules or dissolve them in water. The use of strong CYP3A inhibitors/inducers, and grapefruit and Seville oranges should be avoided for the duration of the study.

If a dose is not taken at the scheduled time, it can be taken as soon as possible on the same day with a return to the normal schedule the following day. The patient should not take extra capsules to make up the missed dose.

The first dose will be delivered in the clinic on Day 1, after which subsequent dosing is typically on an outpatient basis. Ibrutinib will be dispensed to patients in bottles at each visit. Unused ibrutinib dispensed during previous visits must be returned to the site and drug accountability records updated at each visit. Returned capsules must not be redispatched to anyone.

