6.2 Medications to be Used with Caution

6.2.1 CYP3A- Inhibitors/Inducers

Ibrutinib is metabolized primarily by CYP3A. Avoid co-administration with strong CYP3A4 or moderate CYP3A inhibitors and consider alternative agents with less CYP3A inhibition.

- If a strong CYP3A inhibitor (eg, ketoconazole, indinavir, nelfinavir, ritonavir, saquinavir, clarithromycin, telithromycin, itraconazole, nefazadone, or cobicistat) must be used, reduce ibrutinib dose to 140 mg or withhold treatment for the duration of inhibitor use. Subjects should be monitored for signs of ibrutinib toxicity.
- If a moderate CYP3A inhibitor (eg, voriconazole, erythromycin, amprenavir, aprepitant, atazanavir, ciprofloxacin, crizotinib, darunavir/ritonavir, diltiazem, fluconazole, fosamprenavir, imatinib, verapamil, amiodarone, or dronedarone) must be used, reduce ibrutinib to 140 mg (for 840 mg/day dose, reduce to 280 mg) for the duration of the inhibitor use. Avoid grapefruit and Seville oranges during ibrutinib/placebo treatment, as these contain moderate inhibitors of CYP3A (see Section 5.1.3)
- No dose adjustment is required in combination with mild inhibitors.

Avoid concomitant use of strong CYP3A inducers (eg, carbamazepine, rifampin, phenytoin, and St. John's Wort). Consider alternative agents with less CYP3A induction.

A list of common CYP3A inhibitors and inducers is provided in Appendix 3. A comprehensive list of inhibitors, inducers, and substrates may be found at <http://medicine.iupui.edu/clinpharm/ddis/main-table/>. This website is continually revised and should be checked frequently for updates.

For the most comprehensive effect of CYP3A inhibitors or inducers on ibrutinib exposure, please refer to the current version of the IB.

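### The fixed restart doses in Section 4.5 fit only a patient taking 560 mg/day and are not reconciled with the hepatic and CYP3A dose reductions

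*Combined protocol and SAP*

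**What the plan says.** Section 4.0 sets the starting dose: "Ibrutinib will be started at a daily dose of 560 mg po daily". Section 5.1.3 gives the capsule strength: "Ibrutinib 560 mg (4 x 140-mg capsules) is administered orally once daily". Section 4.2 sends dose adjustment for toxicity to Sections 4.4 and 4.5.

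The Section 4.5 table holds the drug at each toxicity and then gives a restart dose. In the related column, the first event reads "Restart at 420 mg/day", the second "Restart at 280 mg/day" and the third "Restart at 140 mg/day"; the fourth stops treatment. The unrelated column runs one step behind. No cell refers to the dose the patient was taking when the toxicity occurred.

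Two other rules place patients below 560 mg for reasons other than a previous toxicity:

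- **Hepatic paragraph, Section 4.5.** For on-study Child-Pugh class A, "the recommended dose reduction for ibrutinib is to a level of 280 mg daily (two capsules"). For class B the recommended level is 140 mg (one capsule). The paragraph ends by pointing to Section 4.5 for dose modification.
- **Section 6.2.1.** With a strong CYP3A inhibitor that must be used, the dose goes to 140 mg or treatment is withheld while the inhibitor is taken. With a moderate one, the instruction is "reduce ibrutinib to 140 mg (for 840 mg/day dose, reduce to 280 mg) for the duration of the inhibitor use".

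No section says which rule takes precedence.

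**The concern.** A table of absolute doses indexed by event count works only if every patient starts the sequence from the same dose. Here the protocol itself moves some patients to 280 or 140 mg before any toxicity is counted. For them, the row for a first related toxicity names a dose above the one at which the toxicity occurred.

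These are patients whose dose was lowered because of liver impairment or an interacting drug. Section 2.8.7 reports a single-dose AUC 2.7-fold higher in Child-Pugh class A and 8.2-fold higher in class B than with normal liver function. The only explicit re-escalation provision in Section 4.5 allows an increase after two cycles without recurrence of the toxicity behind the reduction. An increase at the restart itself, straight after a related toxicity, sits badly with that.

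At stake is the safety of individual patients and the consistency of the dose given after a toxicity.

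**Working it through.** **Inputs.** Starting dose 560 mg/day (Section 4.0). Capsule 140 mg (Section 5.1.3). Related restarts 420, 280, 140 mg/day (Section 4.5 table). Dose already reduced for another reason: 280 mg (class A), 140 mg (class B, Section 4.5), 140 mg (CYP3A inhibitor, Section 6.2.1). The 280 mg figure in Section 6.2.1 belongs to an 840 mg dose, which this trial does not use.

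**Step 1: reproduce the table.** Restart dose after the k-th related event = 560 − 140 × k.

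- k = 1: 560 − 140 = 420
- k = 2: 560 − 280 = 280
- k = 3: 560 − 420 = 140

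This matches the related column exactly, so the column is a one-capsule step-down from 560 mg.

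**Step 2: compare each restart with the dose at the event.** Ratio = table restart dose ÷ dose at which the toxicity occurred, taking that dose to be the reduced level.

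| Related event | Table restart | From 280 mg | From 140 mg |
|---|---|---|---|
| First | 420 mg | 420/280 = 1.5, higher | 420/140 = 3.0, higher |
| Second | 280 mg | 280/280 = 1.0, same | 280/140 = 2.0, higher |
| Third | 140 mg | 140/280 = 0.5, lower | 140/140 = 1.0, same |

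The restart is higher in 3 of 6 combinations, including both at a first related event. In the unrelated column, the second-event restart (420 mg) exceeds both reduced doses, and the third (280 mg) exceeds 140 mg.

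**Step 3: does another instruction block the increase?**

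- *Hepatic case.* The hepatic paragraph sets a level, then refers to Section 4.5. The only rule there for restarting after a toxicity is the table. The class A and B levels are worded as recommendations, and nothing says they cap the table.
- *CYP3A case.* Section 6.2.1 keeps the level at 140 mg while the inhibitor continues. The table says 420 mg for a first related event. Both cannot be followed at once.

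**Step 4: can the situation arise?** Section 3.2.6 excludes patients who require a strong inhibitor or an inducer, but not those on a moderate inhibitor. Section 6.2.1 plans for use of either strength during the study, and the hepatic paragraph plans for impairment that develops on study. Section 4.4 requires a hold for any non-hematologic toxicity of grade 3 or above, among other triggers.

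**The case against.** The strongest reply is that the protocol already contains safeguards. Section 6.2.1 is explicit and time-limited, so a patient still on an inhibitor has a rule requiring 140 mg. If the inhibitor has stopped, that rule lapses and 420 mg is below the 560 mg starting dose. Section 7.3 reserves protocol treatment decisions to the MD Anderson physician and requires approval there, by the physician investigator or a representative, before any dose change. The affected group may be small: strong and moderate inhibitors are to be avoided, and Child-Pugh B or C at screening is excluded.

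Much of this stands. A reader might infer that a patient on a CYP3A inhibitor is simply told to restart higher; the documents do not support that. They give two conflicting instructions, one of which keeps the dose at 140 mg. The ratios also compare doses, not exposures.

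Four further inferences are tempting but unsupported:

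- *That sites will apply the table differently.* Section 7.3 places the decision with one centre.
- *That the toxicity stopping rule is affected.* Section 9.0 counts only grade IV events with a hold longer than two weeks, within four cycles, that persist despite dose reduction. No effect on that count has been shown.
- *That moving between the related and unrelated columns skips a dose level in error.* No section requires one level at a time.
- *That the class C rule, under which patients "must hold study drug until resolved to moderate impairment (Child-Pugh class B) or better", contradicts the table's release condition.* Child-Pugh class and toxicity grade are different scales, and both conditions can be met together.

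What the reply does not answer is the hepatic case, where the text leads back to the table, and the absence of any precedence statement. Physician approval helps, but the approver works from the same conflicting text.

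**Conclusion.** The point holds as a conflict between stated dosing rules. The Section 4.5 table assumes a current dose of 560 mg/day. For a patient reduced to 280 or 140 mg for hepatic impairment, a first related toxicity reads literally as a restart at 1.5 or 3.0 times the dose at which it occurred. A second reads as 2 times from 140 mg and unchanged from 280 mg; a third is never an increase. For a patient on a strong or moderate CYP3A inhibitor, the table and Section 6.2.1 cannot both be followed at a first or second related toxicity while the inhibitor continues.

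This rests on reading the table literally and on the patient being at the reduced level when the toxicity occurs. The documents give no figure for how often that would happen, so no expected number of patients can be stated. Sample size and power are not affected.

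**What to change.** The sponsor should reconcile the Section 4.5 table with the hepatic paragraph and with Section 6.2.1. The protocol should state which rule governs the restart when the patient's current dose is already below 560 mg for a reason other than a previous toxicity. The choice of doses and clinical rules is the sponsor's; none is proposed here.

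Optionally, the Dose Administration eCRF could record the reason for each change (toxicity, CYP3A inhibitor or hepatic impairment). Section 4.5 already requires dose changes to be recorded there, but Section 7.2 says concomitant medication data will not be collected, so an inhibitor-related reduction might not be identifiable later.

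The cost is a protocol amendment to one table and two short passages, plus one eCRF field if the option is taken. It needs no extra patients or visits.

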2.8.7 Pharmacokinetics and Product Metabolism

Following oral administration of ibrutinib at doses ranging of 420, 560, and 840 mg/day, exposure to ibrutinib increased as doses increased with substantial intersubject variability. The mean half life ($t_{1/2}$) of ibrutinib across 3 clinical studies ranged from 4 to 9 hours, with a median time to maximum plasma concentration (T_{max}) of 2 hours. Taking into account the approximate doubling in mean systemic exposure when dosed with food and the favorable safety profile, ibrutinib can be dosed with or without food. Ibrutinib is extensively metabolized primarily by cytochrome P450 (CYP) 3A4. The on-target effects of metabolite PCI-45227 are not considered clinically relevant. Steady-state exposure of ibrutinib and PCI-45227 was less than 2-fold of first dose exposure. Less than 1% of ibrutinib is excreted renally. Ibrutinib exposure is not altered in patients with creatinine clearance (CrCl) >30 mL/min. Patients with severe renal impairment or patients on dialysis have not been studied. Following single dose administration, the AUC of ibrutinib increased 2.7-, 8.2- and 9.8-fold in subjects with mild (Child-Pugh class A), moderate (Child-Pugh class B), and severe (Child-Pugh class C) hepatic impairment compared to subjects with normal liver function. A higher proportion of Grade 3 or higher adverse reactions were reported in patients with B-cell malignancies (CLL, MCL and WM) with mild hepatic impairment based on NCI organ dysfunction working group (NCI-ODWG) criteria for hepatic dysfunction compared to patients with normal hepatic function.

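### Child-Pugh class A liver impairment present at baseline has no starting-dose rule: the patient is eligible and starts at 560 mg, although the protocol recommends 280 mg when class A arises on study

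*Combined protocol and SAP*

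**What the plan says.** **Starting dose.** Section 4.1: "Ibrutinib will be started at a daily dose of 560 mg po daily". Section 5.1.3 repeats it: "Ibrutinib 560 mg (4 x 140-mg capsules) is administered orally once daily". Neither makes an exception for liver function.

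**Entry.** Section 4.5 states that subjects with clinically significant "hepatic impairment at the time of screening (Child- Pugh class B or C) are excluded from study participation". The liver-function criterion in Section 3.1.4 is "AST and/or ALT < 3 times the ULN", and 3.2.7 is its mirror image. Section 3.2.9 excludes active hepatitis B or C infection. No criterion in Section 3 refers to Child-Pugh class.

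**On-study impairment.** Section 4.5 halves the starting dose for class A that arises later: "develop mild liver impairment while on study (Child-Pugh class A), the recommended dose reduction for ibrutinib is to a level of 280 mg". Class B arising on study leads to a recommended 140 mg, and class C to a hold.

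**Toxicity ladder.** In the Section 4.5 table, the instruction after a first drug-related toxicity is "Restart at 420 mg/day", and 280 mg follows a second. If the toxicities are judged unrelated, 280 mg follows a third.

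**Exposure and safety background.** Section 2.8.7 reports that after a single dose "the AUC of ibrutinib increased 2.7-, 8.2- and 9.8-fold in subjects with mild (Child-Pugh class A"), moderate and severe impairment respectively, compared with normal liver function. It adds that Grade 3 or higher adverse reactions were proportionally more frequent in patients with B-cell malignancies and mild impairment, classified by NCI-ODWG criteria.

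**The concern.** Section 4.5 bases its hepatic rules on the drug being metabolised in the liver. That reason applies equally to impairment present on Day 1 and impairment that appears in month 4, yet the dose rule covers only the second case. The first falls back on 4.1 and receives 560 mg.

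The protocol handles another cause of raised exposure differently. Under Section 6.2.1, a patient who must take a moderate CYP3A inhibitor has the dose cut to 140 mg for as long as the inhibitor is used, whenever it was started.

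What is at stake is the safety of a patient who enters with class A impairment. The general safeguards (liver function tests, holds for Grade 3 or higher non-hematologic toxicity, stepwise restarts) respond to abnormality or toxicity once it appears. They do not set a suitable dose at the start.

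**Working it through.** The protocol gives no figure of its own to reproduce. The check is a comparison of the text followed by simple arithmetic.

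**Step 1: is class A at baseline eligible?** Section 4.5 excludes B and C only. Sections 3.1.4 and 3.2.7 limit AST/ALT and are not expressed as Child-Pugh class. Section 3.2.9 concerns infection. Class A is therefore not excluded.

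**Step 2: which dose applies?**

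| Liver status | Governing text | Daily dose |
|---|---|---|
| Class A at screening | 4.1 and 5.1.3 (no hepatic exception) | 560 mg |
| Class A arising on study | 4.5 | 280 mg recommended |
| Class B arising on study | 4.5 | 140 mg recommended |

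Ratio for the same class: 560 / 280 = 2.

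**Step 3: what exposure does that imply?** Inputs are the AUC ratios in Section 2.8.7 (2.7 for class A, 8.2 for class B). Assumptions: AUC is proportional to dose, and the single-dose ratio holds under daily dosing. Equivalent dose in normal liver function = dose × AUC ratio. The reference is 560 mg.

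| Case | Calculation | Equivalent dose | Relative to 560 mg |
|---|---|---|---|
| Class A at baseline, 560 mg | 560 × 2.7 | 1,512 mg | 2.70 |
| Class A, restarted at 420 mg | 420 × 2.7 | 1,134 mg | 2.03 |
| Class A on study, 280 mg | 280 × 2.7 | 756 mg | 1.35 |
| Class B on study, 140 mg | 140 × 8.2 | 1,148 mg | 2.05 |

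Under these assumptions a baseline class A patient at 560 mg has higher expected exposure than a class B patient on the recommended reduced dose (1,512 against 1,148 mg-equivalent).

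**Step 4: how does the 4.5 table bring a baseline class A patient to 280 mg?**
- Related toxicities: 560 → 420 → 280, two events.
- Unrelated toxicities: 560 → 560 → 420 → 280, three events.

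Section 4.5 also lets the investigator re-escalate after two cycles without recurrence. A patient who develops class A on study is recommended 280 mg directly, without climbing this ladder.

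**Step 5: context for 1,512 mg-equivalent.** Section 5.1.4 reports that no MTD was reached at up to 1,400 mg/day (1,512 / 1,400 = 1.08). It also reports single doses of up to 1,680 mg in healthy subjects (1,512 / 1,680 = 0.90), with one reversible Grade 4 transaminase rise at 1,680 mg. Section 2.8.7 accepts an "approximate doubling in mean systemic exposure when dosed with food".

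**The case against.** The strongest reply is that stable class A at entry and new liver decline on ibrutinib are clinically different. New impairment may be harm from the drug, the rule sits under toxicity management, and Section 10.1.1 would ordinarily count the new impairment as an adverse event but not an unchanged pre-existing condition. This weakens the comparison and the CYP3A analogy. It does not remove them, because the reason 4.5 itself gives is hepatic metabolism, which does not depend on when the impairment began.

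Second, harm is not demonstrated. The exposure figures carry a single-dose ratio to daily dosing and assume proportionality, while Section 2.8.7 says only that exposure rose with dose, with wide variation between subjects. This stands: 1,512 mg-equivalent is not shown to be unsafe.

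Third, few patients may be affected. Entrants are in first complete remission, with ECOG status of 2 or better, platelets of at least 75,000 and no active hepatitis B or C. The number with class A is not given and could be zero among 30. This stands too.

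Fourth, other routes lower the dose, and liver tests are frequent: before the first dose, weekly for four weeks, then every two weeks for four weeks. But the other routes, worsening to class B or use of a CYP3A inhibitor, need deterioration or another drug. Neither they nor the tests set a starting dose for stable class A.

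Finally, the Investigator's Brochure or package insert may advise on starting dose. Neither was available, so sites may not have lacked guidance. The protocol's own instruction is still 560 mg.

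**Conclusion.** The concern holds. Class A impairment at screening is eligible, the only starting dose is 560 mg, and the 280 mg recommendation is worded for impairment that develops during the study. The dose is twice that recommended for the same status arising later. Expected exposure is about 2.7 times that of a normal-liver patient on 560 mg, rather than about 1.35 times, if the single-dose AUC ratio and dose proportionality carry over to daily dosing.

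The higher rate of Grade 3 or worse reactions in mild impairment supports caution, although it rests on NCI-ODWG criteria rather than Child-Pugh class. The gap in the text is certain; its clinical consequence is not, and it probably concerns an occasional patient. No effect on the primary endpoint, the sample size or the toxicity stopping rule is claimed. It is a minor to moderate point that should be corrected because the correction is cheap.

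**What to change.** Add to Section 4.1: *Patients with Child-Pugh class A hepatic impairment at screening start at 280 mg daily (two capsules).* Cross-refer to it in Sections 4.5 and 5.1.3.

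An alternative is to add class A to the exclusions in Section 3.2. The 280 mg start is the better default: it uses a dose level the protocol already recommends for this class, needs no new capsule strength and keeps the patient in the study. It is somewhat firmer than the on-study text, which is a recommendation, and the sponsor may soften it to match.

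The cost is one sentence and two cross-references. The Table of Evaluations lists liver function tests but does not name a Child-Pugh assessment. Since 4.5 already excludes classes B and C at screening, the class has to be established then anyway, and no new procedure follows. The downside is a lower dose for an occasional patient, whose expected exposure would still be about 1.35 times the normal-liver value at 560 mg, or the loss of that patient if exclusion is chosen. No statistical figure changes.
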